11.1.2. Baseline and Background Characteristics

All screening and baseline summaries will be based on the Safety Analysis Set unless otherwise indicated.

Ongoing and previous diseases in medical history will be summarised separately by system organ class and preferred term. Coding will be based on MedDRA (the latest available version at study start will be used).

Previous and concomitant medications will only be listed.

11.1.3. Analysis of Efficacy Parameters

The summaries of the efficacy parameters, the statistical analyses of the primary efficacy variable, and the statistical analyses of the secondary efficacy variables will be performed on the Full Analysis Set (primary set for evaluation of superiority of Traumed[®] gel versus placebo, secondary set for evaluation of non-inferiority of Traumed[®] gel compared to diclofenac gel), and on the PP set (primary set for evaluation of non-inferiority of Traumed[®] gel compared to diclofenac gel, secondary set for evaluation of superiority of Traumed[®] gel versus placebo).

Missing values for all efficacy parameters will be imputed by the last observation carried forward (LOCF) approach. In addition, a last percentile carried forward approach (LPCF) will be performed as sensitivity analysis (see also section 11.1.4). Further sensitivity analyses resulting from the blind review of the data will be provided in the final SAP.

All statistical tests will be two-sided with a significance level of $\alpha=0.05$, unless specified otherwise. Where appropriate, statistical tests will be supported by presenting estimates and 95% confidence intervals for the respective treatment effects and differences between the treatment groups. These estimates and confidence intervals will be based on the respective statistical models used for the analysis.

In the study of Schomacher (Schomacher 2008), the clinically relevant difference between VAS scores showed varying results. In the case of low baseline VAS scores the clinically relevant reduction in VAS values starts at 5 to 10 of 100 mm whereas with higher baseline VAS scores minimal change of 20 mm or 30% may be indicated. Nevertheless, the review of Schomacher was not limited to pain of joints of extremities.

In the study of Tubach et al. (Tubach et al. 2005 a/b) the MCII (minimal clinically important improvement) of pain for knee and hip osteoarthritis was evaluated. The absolute (and relative) changes were, respectively, (a) -19.9 mm (-40.8%) and -15.3 mm (-32.0%) for pain.

Based on these, a treatment difference of 16.6 mm seems to be appropriate to show a clinically important improvement for a study with moderate or severe ankle pain. A difference of 16.6 mm on a 0-100 mm VAS scale can be recomputed into a 25 mm x days difference in AUC for pain in VAS score from Day 1 (Baseline) to Day 4 by elementary geometric considerations. In order to assess non-inferiority of Traumed[®] gel with respect to diclofenac gel the non-inferiority margin for comparing the AUCs will be set to 25 mm x days.

Primary Efficacy Variable

Area under the curve (AUC)* for pain on passive movement in Visual Analog Scale (VAS) from baseline to Day 4

*All AUC calculations will be based on actual time of measurement.

Secondary Efficacy Variables

- AUC for pain at rest in VAS from baseline to Day 4
- AUC for pain on passive movement in VAS from baseline to Day 2, 7 and Final Visit
- AUC for pain at rest in VAS from baseline to Day 2, 7 and Final Visit
- Change from baseline of pain on passive movement in VAS to Day 4, 7 and Final Visit
- Change from baseline of pain at rest in VAS to Day 4, 7 and Final Visit
- Change from baseline to Day 2, 4, 7 and Final Visit in the FAAM-ADL subscale
- Amount of rescue medication (doses)
- Time to 50% improvement of pain at rest measured by VAS at patient visits.

Confirmatory Analyses

1. AUC for pain on passive movement in VAS from baseline to Day 4 (test for superiority, Traumed[®] gel versus placebo), Full Analysis Set. The null and alternative hypotheses for the comparison of Traumed[®] gel versus placebo can be formulated as follows:

| |
|--|
| $\begin{aligned} H_0: & \mu_T = \mu_P \\ H_A: & \mu_T \neq \mu_P \end{aligned}$ 
H₀: Null-hypothesis; H_A: Alternative Hypothesis; T: Test Treatment; P: Placebo Treatment; μ: mean of population (AUC)
 |
|--|

2. AUC for pain on passive movement in VAS from baseline to Day 4 (test for non-inferiority, Traumed[®] gel compared to diclofenac gel), Per-Protocol Analysis Set (PP). For the comparison of Traumed[®] gel versus diclofenac gel the null and alternative hypothesis can be formulated as follows:

| |
|--|
| $\begin{aligned} H_0: & \mu_T - \mu_R > 25 \text{ [mm x days]} \\ H_A: & \mu_T - \mu_R \leq 25 \text{ [mm x days]} \end{aligned}$ 
H₀: Null-hypothesis; H_A: Alternative Hypothesis; T: Test Treatment; R: Reference Treatment; μ: mean of population (AUC)
 |
|--|

Hypothesis no. 1 (superiority) is based on the FAS analysis set, while hypothesis no. 2 (non-inferiority) is based on the PP analysis set. This way, both hypotheses are based on the more conservative data set.

If the first *a priori* ordered test (superiority) shows statistical significance, the subsequent hypothesis (non-inferiority) can then be tested individually in a confirmatory manner according to the principle of *a priori* ordered hypotheses (for control of alpha using stepwise testing see [Maurer et al. 1995]).

The confirmatory analyses will be performed using an analysis of covariance (ANCOVA) with baseline pain VAS as covariate. Due to the expected small number of patients per center, an additional inclusion of center as covariate will not be performed (see also EMA Guideline on adjustment for baseline covariates, section 4.2.3., EMA/295050/2013).

Exploratory Analyses

Details for analyzing the secondary efficacy parameters will be given in the SAP. Since all analyses of secondary efficacy parameters are exploratory in nature, no adjustment for multiplicity will be performed. Unless specified otherwise, treatment comparisons for the

secondary efficacy parameters are performed only for Traumed[®] gel versus placebo gel and Traumed[®] gel compared to diclofenac gel, respectively.

Sensitivity Analyses

Several pre-defined sensitivity analyses will be performed in order to demonstrate the robustness of the confirmatory results:

Data Sets

The two primary hypotheses (superiority, non-inferiority) will be evaluated additionally using the corresponding alternative data set (hypothesis no. 1: PP, hypothesis no. 2: FAS). The results of the sensitivity analyses will be compared with the confirmatory results.

Nonparametric Analysis

As a sensitivity analysis to the primary parametric approach, a nonparametric analysis will be performed for the two primary hypotheses.

The nonparametric procedures will be performed by means of the Wilcoxon-Mann-Whitney test. The Wilcoxon-Mann-Whitney test (WMW test) is the well-known robust test attributed to Wilcoxon (Wilcoxon 1945) and Mann and Whitney (Mann et al. 1947); for details of the test see e. g. Armitage, Berry, and Matthews (Armitage et al. 2002), or Sprent and Smeeton (Sprent et al. 2001).

The Mann-Whitney estimator (MW) is the associated effect size measure for the Wilcoxon-Mann-Whitney test (WMW test). It is a robust but highly sensitive effect size measure to determine the magnitude and direction of the treatment effects. It is recommended by many authors for its sensitivity and robustness in all data situations (Agresti et al. 1984, Brunner et al. 2000, Munzel et al. 2003, D'Agostino et al. 2006, Brunner et al. 2013, Kieser et al. 2013) for ordinal scales in non-inferiority trials it is even regarded as the 'gold standard' see, e.g. Design and Analysis of Non-Inferiority Trials (Rothmanns et al. 2011). Technically, the MW gives the probability that a randomly chosen subject of the test group is better off than a randomly chosen subject of the comparison group (with the probability ranging from 0 to 1, with 0.5 indicating equality); it is statistically defined as: $P(X < Y) + 0.5 P(X = Y)$.

The relevant benchmarks for the Mann-Whitney effect size measure (MW) are as follows (Colditz et al. 1988):

| | |
|------|--------------------------|
| 0.29 | large inferiority |
| 0.36 | medium sized inferiority |
| 0.44 | small inferiority |
| 0.50 | equality |
| 0.56 | small superiority |
| 0.64 | medium sized superiority |
| 0.71 | large superiority |

Under the assumption of a normal distribution the defined non-inferiority margin AUC 25 mm x days with common standard deviation 75 mm x days, (see section 11.4) can be re-expressed in terms of the Mann-Whitney statistic: the raw scale margin results in a standardized mean difference of $25/75 = 0.33$, which can be directly transformed to a Mann-Whitney margin of 0.407 (Rahlf's et al. 2014). This margin is consistent with the nonparametric NI bound of 0.40 in a previous NI trial (Gonzalez et al. 2013).

In addition, a non-parametric repeated measurement analysis will be performed by means of the generalized Wilcoxon-Mann-Whitney test (Wei-Lachin procedure), combining the repeated observations by a simultaneous, directional test.

Stratification

In order to control for center effects, a robust stratified analysis will be performed for the primary efficacy criterion applying the Cochran-Mantel-Haenszel procedure with adjustment for centers (CMH pooling, also known as van Elteren pooling). This procedure is robust also with very low sample sizes per center and group.

In order to control for effects of delayed "Day 4" assessments (Day 4+1), a robust stratified analysis (CMH) will be performed for patients with and without delay.

In order to ensure the data integrity of the trial and to exclude potential bias introduced by partial unblinding, a separate analysis of problematic and non-problematic cases will be conducted with subsequent meta-analytic pooling and test for overall effect and heterogeneity.

Further details will be defined in an update of the Statistical Analysis Plan (SAP). (*revised per Amendment to protocol version 3.0*)

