11.4. Determination of Sample Size

Estimation of sample size is based on the primary efficacy variable. A two-sided test of equality of the study drug (Traumed[®] gel) and the comparator (placebo) at level 0.05 based on an expected raw scale treatment difference of AUC 25 [mm x days] and a common standard deviation of AUC 75 [mm x days] for the response variables (re-expressed for nonparametric evaluation in terms of the Mann-Whitney statistic as $MW = 0.6$ (see section 11.1.3), achieves a power of at least 90% for parametric first line analysis as well as for second line nonparametric analysis if the sample size is set to 291 patients for the Traumed[®] gel group and to 146 patients for the placebo group.

Due to an additional safety requirement that AEs with incidence level of 1% for Traumed[®] gel are found during the study with probability 95%, 299 patients for the Traumed[®] gel group are required. Assuming a drop-out rate from the Safety Analysis Set of about 4% an amount of 312 randomized patients in the Traumed[®] gel group is needed. With an allocation ratio of 2:1:1 (Traumed[®] gel : diclofenac gel : placebo) 156 patients are obtained in the diclofenac gel and placebo group each, that is, a total of 624 patients with acute unilateral Grade 1 or Grade 2 sprain of the lateral ankle.

In order to ensure the pre-defined power of the trial for the trial objectives including the confirmatory test for non-inferiority (Traumed[®] gel compared to diclofenac gel), which is based on the Per-Protocol Analysis Set (PP), a sample size enhancement is introduced for compensation of:

- cases for whom maintenance of blinding procedures may have been compromised and, thus, are representing a major protocol violation (exclusion from PP analysis).

For compensation, the final sample size will be enhanced to 202 patients for the diclofenac and Placebo group each, and to 404 patients for the Traumed[®] gel group resulting in a new total of 808 patients. *(revised per Amendment to protocol version 3.0)*

12. Study Report and Publication Policy

An integrated study report in accordance with the ICH Harmonized Tripartite Guideline (E3) (Structure and content of clinical study reports) will be developed.

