Blind data review revealed severe deviations of 'issue' cases from 'non-issue' cases, suggesting that compromised cases might constitute a serious risk of bias, preventing pooled analysis.

The multivariate P-values for the comparison of issue cases vs. non-issue cases regarding the three key domains "Baseline", Efficacy", and "RICE", were throughout below 0.0001, thus, suggesting serious structural differences between issue cases and non-issue cases. The rate of major protocol violations was significantly higher in the group of issue cases (11.4%) as compared to non-issue cases (1.9%; P<0.0001). Also the patient's guess on which treatment he/she received was less balanced in the issue group as compared to the non-issue group (patient's guess for the two active treatments: non-issue cases: 39% Traumed vs. 35% diclofenac, issue cases: 42% Traumed vs. 29% diclofenac).

Final BDRM Decision: In order to preserve the integrity and validity of the trial, issue patients will not be included into the pre-planned confirmatory and secondary analyses of the main part of the Clinical Trial Report. While being evaluated for baseline characteristics, efficacy and safety endpoints in the same way as the non-compromised cases, the compromised cases will be reported separately in the Appendix of the Clinical Trial Report (results to be interpreted with care due to the described issues).

As stated before, the sample size was already proactively increased for compensation in case of an exclusion of the issue patients (Protocol Amendment version 4.0 from February 3, 2020 to Protocol version 3.0). The Reason/Justification for Change of Protocol Section 11.4 (Protocol Amendment version 4.0 from February 3, 2020 to protocol version 3.0) was provided in the Amendment Summary Document for Substantial Protocol Changes (SOC document from February 3, 2020):

The enhancement will ensure planned power and validity for evaluating the pre-defined trial objectives also in case that **only non-compromised cases** allow valid and unbiased conclusions ...

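### Non-inferiority to diclofenac is decided on the PP set alone as the supposedly stricter set, and a failed FAS analysis has no consequence; the risk is small and the remedy cheap

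*Protocol*

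**What the plan says.** Protocol 11.1.3 (Confirmatory Analyses) tests Traumed against placebo on the FAS (hypothesis 1) and non-inferiority to diclofenac, margin 25 mm x days, on the PP set (hypothesis 2). The reason given is one sentence: "This way, both hypotheses are based on the more conservative data set". SAP 9.3.1.1 repeats it.

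The FAS is the secondary set for non-inferiority. Under Sensitivity Analyses (Data Sets), hypothesis 2 is rerun on the FAS, and "The results of the sensitivity analyses will be compared with the confirmatory results". Protocol 11.1.1 and SAP 9.7.1.1 add that relevant FAS/PP differences will be evaluated in the trial report.

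SAP 9.3.1.2 extends the ordered sequence to four hypotheses. Each opens when the preceding test is significant, and no condition on a second analysis set is attached.

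SAP 9.7.1.2 defines the major deviations that remove a patient from PP. They include compliance below 80%, visits outside set windows, a missing Visit 1 or Visit 3 pain score, and premature discontinuation that is not drug-related. Discontinuations for lack of efficacy or adverse events stay in PP. SAP sections 8 and 9.7.1.2 remove the issue patients from all confirmatory analyses.

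**The concern.** A PP set is not stricter by construction. Several exclusion grounds arise after randomisation, so removing those patients can move the Traumed-minus-diclofenac difference either way. If those removed did relatively worse on Traumed, PP is the more lenient set. The FAS can err the other way by diluting a real difference. Neither set protects the claim alone.

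The plan does not say what follows if the two sets disagree. If the PP upper limit is below 25 and the FAS upper limit is not, the rules as written give a confirmatory non-inferiority claim against diclofenac and open hypothesis 3. The discordant FAS result would then be interpreted only after unblinding.

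**Working it through.** **Inputs from the documents.** Two-sided 5% tests (Protocol 11.1.3: "All statistical tests will be two-sided with a significance level of" 0.05), so the upper limit of a two-sided 95% CI is compared with the margin of 25. SD from Protocol 11.4: "a common standard deviation of AUC 75 [mm x days] for the response variables". Major violations in the SAP section 8 rationale: 11.4% in issue cases "as compared to non-issue cases (1.9%; P<0.0001". Final sample 404:202:202, with 184 issue patients.

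**The plan's own figure.** Protocol 11.4 says that, with "the sample size is set to 291 patients for the" Traumed group and 146 on placebo, the test "achieves a power of at least 90% for parametric first line analysis as well as for second line nonparametric analysis". SE = 75 x sqrt(1/291 + 1/146) = 7.61. Power = Phi(25/7.61 - 1.96) = Phi(1.33) = 90.8%. The parametric figure is reproduced.

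**Assumptions needed.**
- 808 - 184 = 624 non-issue patients, split 2:1:1, give 312 Traumed and 156 diclofenac. The documents give no counts by arm.
- The 1.9% rate is taken as the PP exclusion rate, equal in both arms: about 6 and 3 patients, leaving 306:153.
- AUC is normal with SD 75, without covariate adjustment. Hypothesis 2 is taken by itself, ignoring the need to pass hypothesis 1.
- The true difference among excluded patients is not in the documents. A range of 0 to 75 mm x days is used; 75 is one SD and three times the margin.

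**Formulas.**
- SE(FAS) = 75 x sqrt(1/312 + 1/156) = 7.35.
- SE(PP) = 75 x sqrt(1/306 + 1/153) = 7.43.
- Because PP is nested in the FAS, the correlation of the two estimates is SE(FAS)/SE(PP) = 0.99.
- True FAS difference = (306/312) x PP difference + (6/312) x excluded difference.
- P(pass) = Phi((25 - true difference)/SE - 1.96); the probability that both pass comes from the bivariate normal.

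**PP true difference 0, 1.9% excluded.**

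| Difference in excluded patients | True FAS difference | PP passes | FAS passes | Both pass | PP passes, FAS fails |
|---|---|---|---|---|---|
| 0 | 0 | 92.0% | 92.5% | 91.4% | 0.6% |
| 25 | 0.48 | 92.0% | 91.5% | 90.9% | 1.1% |
| 50 | 0.96 | 92.0% | 90.5% | 90.1% | 1.9% |
| 75 | 1.44 | 92.0% | 89.3% | 89.2% | 2.8% |

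In the first row PP is slightly the stricter set, only because it is smaller: FAS passes and PP fails in 92.5 - 91.4 = 1.1%. In the last row the order is reversed: that outcome falls to 89.3 - 89.2 = 0.1%, while PP passes against a failing FAS in 2.8%. With a PP difference of 10 and an excluded difference of 75, the discordant rate is 6.4%.

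**At the margin.** Let the true FAS difference be exactly 25 and the excluded difference 75. The PP difference is then (25 - 0.0192 x 75)/0.9808 = 24.0. PP alone passes with probability Phi((25 - 24.02)/7.43 - 1.96) = 3.4%, against 2.5% for the FAS. Requiring both gives 2.4%.

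**Power cost of requiring both sets, true difference 0 throughout.** At 1.9% excluded: 92.0% to 91.4%, 0.6 points. At 5%: 91.2% to 90.4%, 0.8 points. At 10%: 89.7% to 88.8%, 0.9 points.

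**The case against.** The strongest reply is that the plan already deals with disagreement openly. The FAS analysis of hypothesis 2 is pre-specified, it will be set beside the PP result, and relevant differences will be evaluated in the report. A FAS failure would be visible. This stands: what is missing is the consequence, not the analysis.

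Second, the PP definition is more careful than most. Discontinuations for lack of efficacy or adverse events are kept, which removes the selection most likely to flatter Traumed. Deviations are classified blind, and one criterion, the Visit 1 pain score, is a baseline value. This narrows the room for bias but leaves compliance, visit timing, missing Visit 3 scores and other discontinuations.

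Third, about 9 of 468 patients separate the sets. Even an excluded difference of 75 moves the true FAS difference by only 1.4 mm x days, against an SE of 7.35. This also stands, and it sets the size of the point.

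A reader might infer a serious type I error problem. Taking the same at-margin case with 11.4% excluded, PP alone would claim non-inferiority in about 12.9% of trials; with the 184 issue patients kept in the FAS but not in PP, in about 52%. The documents do not support applying these figures: 11.4% is the rate in issue cases, and the SAP removes issue patients from both sets. Both figures also need the assumed excluded difference of 75.

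**Conclusion.** The point holds as a minor one. Nothing in the documents makes PP the stricter set for hypothesis 2, and no rule links a FAS failure to the claim or to the opening of hypothesis 3. Under the SAP's populations the discordant outcome has a probability of about 0.6% to 2.8% when the PP difference is 0, and the error rate at the margin rises from 2.5% to about 3.4% in the most adverse case tried at 1.9% exclusion. These figures rest on the assumed 312:156 split, SD 75, equal exclusion by arm and the assumed differences in excluded patients. The calculation shows what selection could do; it is not evidence that PP is biased here. The sample size is not affected.

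A reader might also infer that agreement with the FAS would restore the full randomised comparison. It would not. The FAS needs a Grade 1 or 2 sprain and a Day 4 value (LOCF allowed). Patients found to be Grade 3 up to Day 4 leave the efficacy analysis, and issue patients leave both sets.

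**What to change.** In SAP 9.3.1.2, state that non-inferiority under hypothesis 2 is claimed, and the next hypothesis opened, only if the upper limit of the two-sided 95% CI for Traumed minus diclofenac is below the margin in both PP and FAS. Apply the same rule to hypothesis 4 once its own Day 7 margin is stated; the 25 mm x days margin in Protocol 11.1.3 is derived for Day 1 to Day 4.

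List this in SAP section 8 as a change to the Protocol, since the choice of PP as deciding set is Protocol text. Say there that the plan no longer relies on PP being the stricter set, and leave the excerpt in SAP 9.3.1.1 as a faithful citation. Fix the rule before unblinding.

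The cost is small. Both analyses are already planned and no patients are added. Power falls by about 0.6 points at 1.9% exclusion and 0.9 points at 10%. The joint rule cannot raise the type I error, because any trial that passes both sets also passes PP. It does not undo the exclusions common to both sets.

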6.1.2. Assigning Patients to Treatment Groups

Patients will be randomly allocated to Traumed[®] gel or diclofenac gel or placebo gel in 2:1:1 randomisation. A corresponding random code list is prepared using the random permuted block scheme. In accordance with the ICH Biostatistics Guideline, the block size is intentionally not given in the trial protocol [ICH E9 § 2.3.2, “Investigators and other relevant site staff should generally be blind to the block length”]. The sealed random code list and the sets of sealed envelopes are prepared using the validated program RANCODE in a validated working environment at idv Data Analysis and Study Planning, Gauting, Germany.

Patients will be randomised based on the 4-digit randomisation number recorded on the investigational medication (IMP). The next patient eligible for randomisation will be allocated to the lowest available randomisation number at the site. IMP will be provided to all sites in pre-defined shipment blocks and shipment blocks will contain appropriate distribution of randomisation codes belonging to the 3 treatment arms.

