9.3 Evaluations and Endpoints – First Line Analysis

9.3.1 Primary Efficacy Variable

9.3.1.1 Operationalizations in Final Protocol

Primary Efficacy Variable

Area under the curve (AUC)* for pain on passive movement in Visual Analog Scale (VAS) from baseline to Day 4

Confirmatory Analyses

1. AUC for pain on passive movement in VAS from baseline to Day 4 (test for superiority, Traumed[®] gel versus placebo), Full Analysis Set. The null and alternative hypotheses for the comparison of Traumed[®] gel versus placebo can be formulated as follows:

H₀: $\mu_T = \mu_P$ H_A: $\mu_T \neq \mu_P$

H₀: Null hypothesis; H_A: Alternative Hypothesis; T: Test Treatment; P: Placebo Treatment; μ: mean of population (AUC)

2. AUC for pain on passive movement in VAS from baseline to Day 4 (test for non-inferiority, Traumed® gel compared to diclofenac gel), Per-Protocol Analysis Set (PP). For the comparison of Traumed® gel versus diclofenac gel the null and alternative hypothesis can be formulated as follows:

H₀: $\mu_{T} - \mu_{R} > 25 \text{ [mm x days]}$

H_A: $\mu_{\text{T}} \cdot \mu_{\text{R}} \leq 25 \text{ [mm x days]}$

 H_0 : Null hypothesis; H_A : Alternative Hypothesis; T: Test Treatment; R: Reference Treatment; μ : mean of population (AUC)

Hypothesis no. 1 (superiority) is based on the FAS analysis set, while hypothesis no. 2 (non-inferiority) is based on the PP analysis set. This way, both hypotheses are based on the more conservative data set.

If the first *a priori* ordered test (superiority) shows statistical significance, the subsequent hypothesis (non-inferiority) can then be tested individually in a confirmatory manner according to the principle of *a priori* ordered hypotheses (for control of alpha using stepwise testing see [Maurer et al. 1995]).

^{*}All AUC calculations will be based on actual time of measurement.

The confirmatory analyses will be performed using an analysis of covariance (ANCOVA) with baseline pain VAS as covariate. Due to the expected small number of patients per center, an additional inclusion of center as covariate will not be performed (see also EMA Guideline on adjustment for baseline covariates, section 4.2.3., EMA/295050/2013).

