9.4.2.2 Additional Operationalizations

- The robust stratified analyses will be performed for the FAS and PP analysis set as sensitivity analyses for the primary parametric approach by means of the Cochran-Mantel-Haenszel (CMH) pooling procedure with Wilcoxon scores (Peto-Wilcoxon test).
 - Adjustment for centers by means of the CMH pooling procedure will be performed for the area under the curve (AUC) of pain on passive movement in Visual Analog Scale (VAS) from baseline to Day 4 with centers as strata. Small centers will technically be pooled. According to protocol, the final pooling benchmark is to be decided at the time of the blind review of the soft lock data with documentation in the final Statistical Analysis Plan (see ICH Guidance E9 §3.2 "any case decisions concerning this approach should always be taken blind to treatment, for example at the time of the blind review"). Based on the softlock data, the pooling benchmark for small centers is set to N<20 (virtual center labelled as "center 99"). This way, the sensitivity analysis will be based on 12 center strata and one virtual center, which is regarded as reasonable procedural size for the sensitivity analysis.

 - Adjustment for patients with and without delayed "Day 4" assessments (Day 4+1) will be performed for the area under the curve (AUC) of pain on passive movement in Visual Analog Scale (VAS) from baseline to Day 4.
- Due to serious risk of bias, the "problematic" cases will be evaluated separately and will not be part of the confirmatory or secondary analyses (for details, see section 8 Changes to the Protocol).
- Test Procedures: TESTIMATE V6.5.14; PROC PETO-WILCOXON-TEST.

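### The confirmatory ANCOVA omits centre, although numbers are in practice blocked by site and the SAP already holds a workable centre factor; this may cost some precision but does not raise the false-positive risk

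*Protocol*

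**What the plan says.** On the model, Protocol 11.1.3 states: "The confirmatory analyses will be performed using an analysis of covariance (ANCOVA) with baseline pain VAS as covariate". Centre is left out on purpose: "Due to the expected small number of patients per center, an additional inclusion of center as covariate will not be performed". SAP 9.3.1.1 carries the same sentence ("an additional inclusion of center as covariate will not be performed") in a document that, by its section 3, is finalised after hard lock and before unblinding.

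On allocation, Protocol 6.1.2 says: "A corresponding random code list is prepared using the random permuted block scheme". The list is supplied to sites in pre-defined blocks, and "shipment blocks will contain appropriate distribution of randomisation codes belonging to the 3 treatment arms". The next eligible patient is "allocated to the lowest available randomisation number at the site".

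On centre in the analysis, Protocol 11.1.3 plans a Cochran-Mantel-Haenszel (van Elteren) analysis stratified by centre. SAP 9.4.2.2 specifies it with Wilcoxon scores, sets the small-centre cut-off at fewer than 20 patients from softlock data, and reports that "the sensitivity analysis will be based on 12 center strata and one virtual center", a size it calls reasonable.

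**The concern.** Arms that are balanced within centre by the allocation mechanism share the same mix of centres. Variation between centres then largely cancels from the treatment difference, but a model without centre still counts it in the residual variance. The reported standard error is larger than the true one, so the test is conservative and the interval wider than needed. Centre differences are plausible here: the investigator provokes the pain by moving the ankle (Protocol 8.1), and sites range from trauma centres and emergency units to general practices (Protocol synopsis).

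Two things make this worth raising. First, the only reason written out for leaving centre out is a forecast that the SAP could have checked and did not update, although it had already built a centre factor. Second, the planned centre-adjusted analysis is on ranks. It yields no adjusted difference or confidence interval in mm x days, the scale on which non-inferiority is decided.

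**Working it through.** **Inputs from the documents.** Difference 25 and SD 75 mm x days, two-sided 5%, power at least 90%, 291 Traumed and 146 placebo patients, first total 624, enlarged total 808 (Protocol 11.4); about 35 sites (synopsis); margin 25 mm x days (Protocol 11.1.3); 184 issue patients, excluded from the confirmatory analyses (SAP 8 and 9.7.1.2); 12 centres plus one pooled centre (SAP 9.4.2.2).

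**Assumed.** The ICC, meaning the share of residual variance that lies between centres. The documents give none, so I use 0 to 0.20.

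**1. The plan's own figure.** Placebo n = (1.96 + 1.2816)² × 75² × (1 + 1/2) / 25² = 141.8, so 142 placebo and 284 Traumed. At the stated 146 and 291, SE = 75 × √(1/291 + 1/146) = 7.61 and power = Φ(25/7.61 − 1.96) = 90.8%. The stated size reproduces, slightly on the generous side.

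**2. Patients per centre.** 624/35 = 17.8, about 9:4.5:4.5 by arm. 808/35 = 23.1. Without the issue patients, 808 − 184 = 624, again 17.8. The 12 larger centres hold at least 12 × 20 = 240 patients.

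**3. Effect of full centre adjustment.** 624 patients at 2:1:1 give 312 against 156. SE without centre = 75 × √(1/312 + 1/156) = 7.35. With balance within centre, the true SE is 7.35 × √(1 − ICC). It follows that:
- excess interval width = 1/√(1 − ICC) − 1
- type I error without centre = 2Φ(−1.96/√(1 − ICC))
- power without centre = Φ((25/7.35 − 1.96)/√(1 − ICC))
- power with centre = Φ(25/(7.35 × √(1 − ICC)) − 1.96)

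| Assumed ICC | 95% half-width without centre | with centre | Excess width | Type I error without centre | Power without / with |
|---|---|---|---|---|---|
| 0 | 14.41 | 14.41 | 0% | 5.0% | 92.5% / 92.5% |
| 0.05 | 14.41 | 14.05 | 2.6% | 4.4% | 93.0% / 93.7% |
| 0.10 | 14.41 | 13.67 | 5.4% | 3.9% | 93.5% / 94.8% |
| 0.20 | 14.41 | 12.89 | 11.8% | 2.8% | 94.6% / 96.7% |

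**4. Effect of the SAP's pooled factor.** Pooling leaves differences among the small sites in the residual, so the gain is smaller than in step 3. Simulation: 4,000 replicates per scenario, 624 patients, complete blocks of 4 within site, no baseline covariate, Traumed against placebo. The assumed centre sizes are 12 centres of 36 and 24 sites of 8, the latter pooled. Simulation error on a 5% rate is about 0.3 percentage points.

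| Assumed ICC | Half-width without centre | 13-level factor | Narrower by | Type I error without / with | Power without / with |
|---|---|---|---|---|---|
| 0 | 14.44 | 14.44 | 0% | 5.2% / 5.2% | 92.8% / 92.9% |
| 0.05 | 14.43 | 14.19 | 1.7% | 4.4% / 4.8% | 93.3% / 93.9% |
| 0.10 | 14.41 | 13.92 | 3.4% | 3.8% / 4.3% | 92.9% / 93.9% |
| 0.20 | 14.38 | 13.40 | 6.8% | 3.0% / 3.9% | 94.5% / 96.1% |

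**5. If the list were not blocked by site.** In one run at ICC 0.10 under the null, the type I error was 5.1% without centre and 5.4% with it, both compatible with 5%; the half-width fell from 14.41 to 14.11. The conservatism depends on balance within site. Without that balance there is still no sign of inflation from omitting centre.

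**The case against.** The strongest reply is that this is a disclosed, reasoned choice with small consequences. Much of it stands.

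- **The forecast.** A reader might infer that the SAP's count contradicts the protocol's reason. It does not. The protocol speaks of an expectation, about 18 patients per site at 624 patients, and about 18 again once 184 issue patients are removed. The SAP confirms that centres below 20 exist, and a centre of 20 has only about 10:5:5. What remains is that the final SAP repeats the forecast without testing it against its own counts.
- **Width.** A reader might also infer that the planned intervals are in fact too wide. That needs centre variance left after baseline adjustment, which the documents do not quantify. Baseline VAS is obtained by the same manoeuvre and will absorb part of a stable investigator effect; goniometer control and joint training (Protocol 8.1) reduce it further.
- **Balance.** It is inferred. Protocol 6.1.2 speaks of an appropriate distribution, not of stratification by centre, and does not equate shipment blocks with randomisation blocks. Removing issue patients may disturb balance. Hence approximately balanced, and no stronger.
- **Existing cover.** A centre-stratified analysis is planned, and the plan re-expresses the margin as a Mann-Whitney value of 0.407. But that conversion assumes normality and an SD of 75, and SAP 9.4.2.2 does not say that the stratified result is compared with it.
- **Size.** Power without centre stays above 90% in every scenario, and the error is on the safe side. This limits the weight of the point. It is no reason to leave out a factor that showed no widening at ICC 0.

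**Conclusion.** The point holds as a low-cost improvement in precision. The plan allocates in a way that approximately balances arms within centre, has a blinded 13-level centre factor, and does not use it in the model that decides the trial. The reason given was sound as a forecast, but the final SAP restates it without updating it. If centres differ after baseline adjustment, the confirmatory interval is conservative. At assumed ICCs of 0.05 to 0.10 it is 2.6% to 5.4% wider than under full centre adjustment, and the SAP's pooled factor would narrow the half-width by about 1.7% to 3.4%. If centres do not differ, nothing is lost either way.

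These sizes rest on the assumed ICC range, SD 75, 312 against 156 patients, near balance within site and, for the pooled factor, assumed centre sizes. It would be wrong to conclude that the confirmatory tests are invalid or that a positive result would be suspect on this ground: the type I error without centre is at or below the nominal level wherever balance holds, and the non-inferiority interval errs towards not concluding non-inferiority.

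**What to change.** Before unblinding, amend SAP 9.3.1.2 so that the confirmatory ANCOVA includes the centre strata of SAP 9.4.2.2 as a fixed main effect, next to treatment and baseline VAS. The SAP's confirmatory model has separate regression lines per group, so say explicitly that centre enters as a main effect without a treatment interaction; the adjusted group difference at the common baseline value then does not depend on how centres are weighted.

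SAP 9.4.2.2 does not say whether its softlock count includes the issue patients. Confirm the fewer-than-20 pooling rule blind on the non-issue patients actually analysed, and fix the resulting strata in the SAP. Record the change in SAP section 8, and keep the ANCOVA without centre as the sensitivity analysis. If the sponsor prefers to retain the planned model, the minimum is to justify the omission from actual counts and to add a centre-adjusted ANCOVA reporting the difference and interval in mm x days.

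Cost: 12 degrees of freedom out of about 465, a respecified model statement, and a documented departure from the protocol wording. No new data are needed. This SAP already changes the confirmatory sequence before unblinding by adding Day 7, so one further recorded change is a small burden.
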